1.3 SCHEDULE OF ACTIVITIES (SOA)

	Screening		Intervention Period ^b							Participants who prematurely discontinued IMP		Participants who did not prematurely discontinue IMP		Notes
	Month		0	3	6	9	12/ 24/ ...	15/21/ 27/ ...	18/30/ ...					
Week	-3	-1	0	12	24	36	48/96/ ...	60/84/ 108/...	72/120/ ...					
Visit	1	2	3 R	4	5	6 ☎	7/11/...	8/10/12/... ☎	9/13/...	pEOT ^c	Study closeout ^d	Study closeout ^d	Follow-up	
Acceptable range (days)	+7 ^a	± 3 ^a		± 7	± 7	± 7	± 7	± 7	± 7				Closeout + 6 weeks	
Informed consent	X													
Inclusion and exclusion criteria	X		X											
Demography	X													
Physical examination	X		X				X			X		X		
Medical/surgical history	X													
Vital signs	X	X	X	X	X		X		X	X	X	X		
Height	X									X		X		
Body weight	X		X	X	X		X		X	X	X	X		
Ophthalmologic exam with fundoscopy	X ^e													

Month	Screening		Intervention Period ^b							Participants who prematurely discontinued IMP		Participants who did not prematurely discontinue IMP		Notes
			0	3	6	9	12/ 24/ ...	15/21/ 27/ ...	18/30/ ...					
Week	-3	-1	0	12	24	36	48/96/ ...	60/84/ 108/...	72/120/ ...					
Visit	1	2	3 R	4	5	6 ☎	7/11/...	8/10/12/... ☎	9/13/...	pEOT ^c	Study closeout ^d	Study closeout ^d	Follow-up	
Acceptable range (days)	+7 ^a	± 3 ^a		± 7	± 7	± 7	± 7	± 7	± 7				Closeout + 6 weeks	
12-lead ECG			X	X						X		X		Recording at Week 0 (Visit 3) should be obtained prior to first dose of double-blind IMP
Randomization			X											
Interactive response technology (IRT) contact	X	X	X	X	X		X		X	X	X	X	X	
Injection training/retraining and self-injection at site		X												
IMP dispensed			X	X	X		X		X					
IMP accounting				X	X		X		X	X		X		
IMP compliance				X	X	X	X	X	X	X		X		
Concomitant medication review	X	X	X	X	X	X	X	X	X	X	X	X		
AE and SAE review	←=====→													

	Screening		Intervention Period ^b							Participants who prematurely discontinued IMP		Participants who did not prematurely discontinue IMP		Notes
Month			0	3	6	9	12/ 24/ ...	15/21/ 27/ ...	18/30/ ...					
Week	-3	-1	0	12	24	36	48/96/ ...	60/84/ 108/...	72/120/ ...					
Visit	1	2	3 R	4	5	6 ☎	7/11/...	8/10/12/... ☎	9/13/...	pEOT ^c	Study closeout ^d	Study closeout ^d	Follow-up	
Acceptable range (days)	+7 ^a	± 3 ^a		± 7	± 7	± 7	± 7	± 7	± 7				Closeout + 6 weeks	
Laboratory assessments													Laboratory assessments performed at Week 0 (Visit 3) should occur prior to first dose of double-blind IMP	
HbA1c	X			X	X		X		X	X		X		
HBsAg and HCAb	X													
Hematology ^f	X		X	X	X		X		X	X	X	X	X	

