9.4.2 Safety analyses

All safety analyses will be performed on the Safety Population.

The **observation period of safety data** is divided into 3 main segments:

- The pre-treatment period is defined as the time from informed consent up to the time of the first injection of IMP
- The on-treatment period is defined as the time from the first injection of IMP up to 30 days after the last injection of IMP
- The post-treatment period is defined as the time starting 31 days after the last injection of IMP (after the on-treatment period)

The AE observations will be classified per the observation periods of safety data as defined above into:

- **Pre-treatment AEs** are AEs that developed or worsened or became serious during the pre-treatment period
- **Treatment-emergent AEs** are AEs that developed or worsened or became serious during the on-treatment period
- **Post-treatment AEs** are AEs that developed or worsened or became serious during the post-treatment period.

The primary focus of AE reporting will be on TEAEs. Pre-treatment and post-treatment AEs will be described separately.

In addition to the on-treatment period, all AEs, SAEs, AEs leading to permanent treatment discontinuation, and AEs leading to death will be summarized for the on-study period, which is defined as the time from randomization up to the day of recorded end of study or last contact.

Table 8 - Safety analyses

Endpoint	Statistical Analysis Methods
AE	All AEs will be coded to a lowest level term (LLT), preferred term (PT), high level term (HLT), and high level group term (HLGT) and associated SOC using the version of MedDRA currently in use by the Sponsor at the time of DB lock.
SAE	
AE leading to treatment discontinuation	Adverse event incidence tables will be presented by primary SOC (sorted by internationally agreed order), HLGT, HLT and PT (sorted in alphabetical order) for each treatment group, showing the number (n) and percentage (%) of participants experiencing an AE.
AE leading to death	Adverse event incidence table will be provided by treatment group for all types of TEAEs: all TEAEs, all treatment emergent SAEs, all TEAEs leading to permanent treatment discontinuation, all TEAEs leading to death, all AESI, and AE requiring specific monitoring.
AESI	
AE requiring specific monitoring	

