#### ***Observation period***

The observation period will be divided into 3 periods:

- The pre-treatment period or screening period is defined as the time from signed informed consent up to the time of first injection of the double-blind IMP
- The treatment-emergent adverse event period (on-treatment period) is defined as the time from the first injection of the IMP to the last injection of the IMP + 30 days (or +7 days for hypoglycemia).
- The posttreatment period is defined as the period after the end of the treatment-emergent adverse event period.

The on-study observation period/on-study is defined as the time from first IMP until the end of (the) study date (defined as the last scheduled visit for those who completed the study and the study discontinuation date collected on eCRF form 'Completion of End of Study' for those who did not complete the study. If death is reason collected on the 'Completion of End of Study' form, date of death will be used).

The post-study observation is defined as anything after the on-study observation period.

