#### **2.3.3.1 Extent of investigational medicinal product exposure**

The extent of IMP exposure will be assessed in the safety population by duration of IMP exposure and by category.

Duration of IMP exposure is defined as last dose date – first dose date + 7 day, regardless of unplanned intermittent discontinuations (see [Section 2.5.3](#) calculation in case of missing or incomplete data).

Duration of IMP exposure will be summarized descriptively as a quantitative variable (number, mean, SD, median, minimum, and maximum). In addition, duration of treatment exposure will also be summarized by numbers and percentages for each category and cumulatively. Following are the categories of exposure-range (in months): <3 months, >3 to 6 months, >6 to 12 months, >12 to 18 months, >18 to 24 months, > 24 to 36 months, > 36 months.

Additionally, the cumulative duration of treatment exposure will be provided, defined as the sum of the duration of treatment exposure for all patients, and will be expressed in patient years.

Percentage of injection taken will be summarized, calculated as (total number of planned injections – number of missed injections)/total number of planned injections\*100 during treatment period.

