### ***General common rules***

All safety analyses will be performed on the safety population as defined in [Section 2.2.4](#), unless otherwise specified, using the following common rules:

- Safety data in patients who do not belong to the safety population (e.g., exposed but not randomized) will be listed separately
- For WBC and differential counts, the baseline is defined as the last available value before the first injection of IMP where no differential component is missing.
- The potentially clinically significant abnormality (PCSA) values are defined as abnormal values considered medically important by the Sponsor according to predefined criteria/thresholds based on literature review and defined by the Sponsor for clinical laboratory tests, vital signs, and ECG (PCSA version dated May 2014 [[Appendix A](#)])
- PCSA criteria will determine which patients had at least 1 PCSA during the on-treatment period, taking into account all evaluations performed during the on-treatment period, including unscheduled or repeated evaluations. The number of all such patients will be the numerator for the on-treatment PCSA percentage
- The treatment-emergent PCSA denominator by group for a given parameter will be based on the number of patients assessed for that given parameter during the on-treatment period by treatment group in the safety population.
- For laboratory and vital sign parameters defined as efficacy endpoints, descriptive statistics and graphs will be provided in the efficacy section only, and PCSAs summaries will be provided in the safety section.
- For quantitative safety parameters based on central laboratory/reading measurements, descriptive statistics will be used to summarize results and change from baseline values by visit and treatment group. Summaries will include the last on-treatment value. The last on-treatment value is defined as the value collected on the same day/time of the last injection of IMP. If this value is missing, this last on-treatment value will be the closest value prior to the last injection of IMP.
- The analysis of the safety variables will be essentially descriptive, and no statistical hypothesis testing is planned.

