### **2.3.5.3 Analyses of laboratory variables**

This section will be organized by biological function as specified in [Section 2.1.4.3](#).

The summary statistics (including number, mean, median, standard deviation, minimum and maximum) of all protocol-required laboratory variables (central laboratory values, changes from baseline and/or percent change from baseline [e.g., lipid parameters, albumin, total protein, hemoglobin, hematocrit]) will be calculated for each visit or study assessment (baseline, each post-baseline time point, last on-treatment value) by treatment group. For selected laboratory parameters (eg, ALT, AST, and ALP), descriptive statistics will also be summarized by upper limit of normal (ULN) values. Graphical presentations will be used to examine trends over time using mean ( $\pm$ SE) and/or mean change from baseline ( $\pm$ SE) at scheduled visits. Results will be presented in standard international unit.

The incidence of PCSAs (list provided in [Appendix A](#)) at any time during the treatment-emergent adverse event period will be summarized by biological function and treatment group whatever the baseline level and/or according to the following baseline status categories:

- Normal/missing
- Abnormal according to PCSA criterion or criteria

For parameters for which no PCSA criteria are defined, similar table(s) using the normal range will be provided as necessary. For calcitonin, no PCSA criterion is defined. Similar summaries will be provided using the pre-defined categories:  $\leq$ ULN,  $>$ ULN - 20 ng/L,  $\geq$ 20 -  $<$ 50 ng/L, and  $\geq$ 50 ng/L (Note that ng/L is the standard international unit and is equivalent to pg/mL).

All measurements collected during the On-treatment period, including values from unscheduled visits, will be considered for the PCSA summaries. However, when several measurements are performed on the same date and at the same time for a given laboratory test, the central laboratory value will be selected over the local lab value. These summaries will include patients in the safety population who have at least 1 assessment performed during the On-treatment period. When a PCSA definition involves a change from baseline value, patients must also have a baseline value to be included in the summaries, and when required by the definition of the abnormality, patients must also have available laboratory normal ranges.

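### The SAP's last on-treatment laboratory value can be a pre-dose sample, and it leaves out samples that the SAP itself counts as on treatment

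*SAP*

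**What the plan says.** The rule is in SAP 2.3.5, General common rules: "The last on-treatment value is defined as the value collected on the same day/time of the last injection of IMP". The fallback follows: "If this value is missing, this last on-treatment value will be the closest value prior to the last injection of IMP". Neither sentence sets a lower limit at the first dose.

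The SAP draws the on-treatment period differently. Section 2.1.4 has it "defined as the time from the first injection of the IMP to the last injection of the IMP + 30 days", and Protocol 9.4.2 agrees: "The on-treatment period is defined as the time from the first injection of IMP up to 30 days after the last injection of IMP". Exposure has a third end point, in SAP 2.3.3.1: "last dose date – first dose date + 7 day".

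The value is used in SAP 2.3.5.3, where laboratory summaries are produced for "baseline, each post-baseline time point, last on-treatment value) by treatment group". The same section flags it as high or low in the listings. SAP 2.5.5 lets unscheduled measurements supply it.

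On sampling, the Protocol 1.3 schedule puts chemistry and hematology at screening, Weeks 0, 12, 24, 48, 72 and so on, then at premature end of treatment (pEOT), close-out and follow-up. The Week 0 sample is pre-dose: "Laboratory assessments performed at Week 0 (Visit 3) should occur prior to first dose of double-blind IMP".

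**The concern.** A value labelled last on-treatment should come from a time when the participant had been exposed to drug, and should be the latest such value. The rule can fail on both counts. With no lower limit, a sample drawn before any drug was given can be reported as on-treatment. With the upper limit at the last injection, the pEOT sample is normally excluded, because that visit follows the decision to stop. Yet it is often the sample closest to the reason for stopping.

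Safety is a secondary objective, and this statistic is requested across the protocol-required laboratory variables. Protocol 2.3 reports that discontinuations, nausea and vomiting in Phase 2 appeared dose dependent, and titration runs to Week 8. Early stops are therefore likely to be more frequent on active drug. Artificial zeros would then fall more heavily on the active arms and pull their mean changes toward no effect.

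**Working it through.** No figure in the plan needs reproducing. The check applies the rule to the sampling schedule and compares the result with the SAP's own on-treatment period.

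**1. Which samples qualify**

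| Sample | Eligible under SAP 2.3.5? | Inside the SAP 2.1.4 on-treatment period? |
|---|---|---|
| Week 0, pre-dose | Yes, if nothing later precedes the last injection | No |
| pEOT, 1–30 days after last injection | No | Yes |
| Close-out on IMP, last injection that day | Yes | Yes |
| Close-out on IMP, last injection 1–7 days earlier | No | Yes |
| Close-out after a premature stop (at least 6 weeks = 42 days) | No | No |

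Rows 1, 2 and 4 are contradictions. Row 5 is consistent: 42 days exceeds 30, so those samples are properly off treatment.

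**2. Early stops**

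Inputs: weekly injections on days 0, 7, 14 and so on; scheduled samples on days 0 and 84; no unscheduled sample. A last injection at any of Weeks 0 to 11 (1 to 12 doses, days 0 to 77) returns the day 0 sample. A last injection at Week 12 (day 84) returns the Week 12 sample. Moving the Week 12 visit within its ±7-day window puts 11, 12 or 13 injections before the sample.

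Example: last injection at Week 4 (day 28), pEOT assumed 7 days later (day 35). The rule returns day 0. The on-treatment period runs to day 28 + 30 = 58, so it would return day 35.

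**3. Change from baseline for these participants**

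SAP 2.1.1 generally sets baseline as the last value before the first dose. If that is the Week 0 sample, change = W0 − W0 = 0. For creatinine and eGFR, baseline is the mean of all pre-dose central values. With one screening value S and one Week 0 value W0, change = W0 − (S + W0)/2 = (W0 − S)/2. That is near zero but not exactly zero, and contains no drug effect.

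**4. Participants on IMP at close-out**

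If the last injection is on the close-out day, the lag is 0. If it is 1 to 7 days earlier, the rule goes back to the previous on-site sample. With close-out spread evenly over Weeks 104 to 156 (assumption), that sample lies on average 11.7 to 11.8 weeks, and at most 23.9 weeks, before the last injection.

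**5. Size**

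Efpeglenatide participants: 4,000 × 2/3 ≈ 2,667. Let f be the share stopping before the Week 12 sample with no unscheduled post-dose value. If their actual mean change is D, the arm mean loses f × D. If D equals that of the other participants, the dilution is the fraction f.

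| Assumed f | Participants (2,667 × f) | Dilution of mean change |
|---|---|---|
| 2% | 53 | 2% |
| 5% | 133 | 5% |
| 10% | 267 | 10% |

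The documents do not give f. The nearest figures are in Protocol 2.3: gastrointestinal discontinuations of 2.2% to 9.8% in the large Phase 2 studies. If all such stops fell before Week 12 (an extreme assumption, covering that reason only), this would be 59 to 261 participants.

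**The case against.** The strongest counter-argument is that this is one descriptive statistic, that most data survive elsewhere, and that stopping at the last injection deliberately avoids off-drug samples. Much of that is fair, and it rules out several stronger readings.

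- **pEOT and close-out data are thrown away.** A reader might infer this, but the loss is to this statistic alone. Values within 30 days of the last injection still enter the tables of potentially clinically significant abnormalities (PCSA), and participants with such an abnormality have their profile listed.
- **Anyone stopping before Week 12 shows zero change.** Unscheduled values count under SAP 2.5.5, and Protocol 7.1.1 and Appendix 6 call for rechecks of abnormal results. Those help only if drawn on or before the last injection, which will vary by case.
- **Six in seven completers lose their close-out sample.** That follows only if the close-out day is unrelated to the injection day. Protocol 4.1 times the follow-up visit from the last dose and Protocol 4.4 times it from close-out, both at 6 weeks. Together they put last dose and close-out at about the same time. The antibody row of the schedule also foresees dosing at the site. The documents do not fix how often the two days differ.
- **Vital signs are equally affected.** The SAP's vital signs are heart rate and blood pressure, both exploratory efficacy endpoints (2.1.3.3). The General common rules send descriptive statistics for such parameters to the efficacy section only. SAP 2.4.4.1 nevertheless asks for a last on-treatment value. That conflict has to be settled before any effect on vital signs can be claimed.

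It can also be said that the words on-treatment already exclude pre-dose values. A programmer could read them so, but the derivation does not say it, and two programmers could produce different tables. The preference for on-drug samples does not explain the missing lower limit, nor the mismatch with a period the SAP already calls on treatment.

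**Conclusion.** The point holds for laboratory parameters with no scheduled sample between the pre-dose Week 0 visit and Week 12. As written, the rule returns a pre-dose value for early stoppers without an unscheduled post-dose sample, and it excludes pEOT samples taken within 30 days after the last injection. For participants still on IMP at close-out, the sample is lost only when the last injection was on another day, at a frequency the documents leave open.

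The impact is modest: the last on-treatment laboratory summaries and the matching listing flags. No hypothesis test, alpha or sample size is touched. The dilution figures rest on assumed stopping rates, visits on nominal days and stoppers resembling the others. A larger true change among stoppers would make the loss greater. That active arms would be affected more is an inference from the Phase 2 pattern. The rule should still be corrected, because it gives a wrong descriptive safety result and the repair is trivial.

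**What to change.** In SAP 2.3.5, define the last on-treatment value as the last measurement taken after the first injection and no later than the end of the section 2.1.4 on-treatment period (last injection + 30 days). State that a participant with no such measurement is missing for this statistic, and show the number contributing. Apply the definition to the summaries and listing flags in 2.3.5.3. The 30-day limit is preferable to the 7-day exposure limit because it matches the PCSA window.

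Separately, reconcile the General common rules with 2.4.4.1 on where heart rate and blood pressure statistics are reported and whether a last on-treatment value is wanted for them.

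The cost is one SAP sentence and one derivation flag, with no new data. The downside is that some values will come from up to 30 days after the last dose, which the SAP already classes as on treatment. Some early stoppers will move from a zero change to missing.

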#### ***2.3.5.1 Analyses of adverse events***

##### ***Generalities***

The primary focus of AE reporting will be on TEAEs. Pretreatment and posttreatment adverse events will be described separately.

If an adverse event date/time of onset (occurrence, worsening, or becoming serious) is incomplete, an imputation algorithm will be used to classify the adverse event as pretreatment, treatment-emergent, or posttreatment. The algorithm for imputing date/time of onset will be conservative and will classify an adverse event as treatment emergent unless there is definitive information to

determine it is pretreatment or posttreatment. Details on classification of adverse events with missing or partial onset dates are provided in [Section 2.5.3](#).

Adverse event incidence tables will present by SOC and PT, sorted in alphabetical order for each treatment group, the number (n) and percentage (%) of patients experiencing an adverse event. Multiple occurrences of the same event in the same patient will be counted only once in the tables within a treatment phase. The denominator for computation of percentages is the safety population within each treatment group.

Sorting within tables ensures the same presentation for the set of all adverse events within the observation period (pretreatment, treatment-emergent, and posttreatment). For that purpose, the table of all TEAEs presented by SOC and PT sorted by the internationally agreed SOC order and decreasing frequency of PTs within SOCs will define the presentation order for all other tables unless otherwise specified. Sorting will be based on incidence in the pooled efpeglenatide group.

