- Gastrointestinal AEs, in particular, nausea, were the most common. The trend over time for nausea and vomiting events appeared dose related with an increase after the first injection, and generally decreasing thereafter. In studies where a titration phase (ie, where a schedule of gradual dose escalation up to the randomized dose) occurred, the effect was less pronounced during the titration phase. The percent of TEAEs, discontinuations and nausea and vomiting appeared to be dose dependent.
- There were no reports of pancreatitis.

- TEAEs leading to discontinuation in the GI disorders system organ class (SOC) for efpeglenatide in Studies HM-EXC-203, HM-EXC-204 and HM-EXC-205 (the large Phase 2 studies) were 2.2%, 8.3% and 9.8%, respectively.
- There was one case of medullary thyroid cancer and one case of pancreatic cancer reported in the Phase 1 and 2 programs. They were considered by the investigators to be unrelated or unlikely related to efpeglenatide respectively.
- No serious or severe immunogenicity events (eg, allergic reactions or immune complex disease and injection site reactions) were reported.
- No severe hypoglycemia was reported.
- No fetal toxicity was reported.
- Elevated ALT levels ≥ 3 x upper limit of normal (ULN) post-baseline were seen in 15 of 754 subjects in the large Phase 2 studies (HM-EXC-203 and HM-EXC-204 in patients with T2DM and HM-EXC-205 in obese subjects); 2 of 147 subjects on placebo, 12 of 571 subjects on efpeglenatide, and 1 of 36 subjects on liraglutide. There were several confounding factors such as acetaminophen (paracetamol) used and elevated levels at either baseline or screening. None of these subject experienced increased bilirubin >2 x ULN. Four of the 15 subjects discontinued study medication due to abnormal liver function tests. There were no cases of ALT increase ≥ 3 x ULN in the Phase 1 studies (HM-EXC-101 and HM-EXC-102) and the Phase 2 studies (HM-EXC-201 and HM-EXC-202).
- Diabetic retinopathy complications have been reported for one of GLP-1 RAs (as of 05 December 2017). No case has been reported for efpeglenatide.
- The 24-hour ECG performed in Study HM-EXC-102 showed that the increase of heart rate (HR) seen with 6 mg efpeglenatide was in the range of liraglutide 1.8 mg.
- There were no deaths in the studies.

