#### ***Analysis of on-study AEs***

- All the analyses in above categories, including AEs, SAEs, AEs leading to permanent treatment discontinuation, and AEs leading to death will be summarized for the on-study period by SOC and PT.

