#### ***Analyses of events of special interest and events requiring specific monitoring***

Unless otherwise specified, AESI and AERSM will be summarized during the TEAE period by prespecified- grouping (AE category of interest) and PT, showing the number (%) of participants, sorted by decreasing frequency of PT.

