#### **Severe hypoglycemia**

The severe hypoglycemia will be analyzed on TEAE period.

The following analysis will be provided for severe hypoglycemia:

- Number (%) of patients with at least one severe hypoglycemia
- Number of events per 100 patient-years of total IMP exposure.

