### Pancreatic events

The Pancreatic events will be reviewed, assessed and/or adjudicated by CEC.

The following analysis will be provided for positively adjudicated events during the TEAE period:

- The number (%) of patients with at least one positively adjudicated pancreatitis by type: 1) acute pancreatitis, 2) acute on chronic pancreatitis, 3) chronic pancreatitis, 4) unknown pancreatitis;
- The number (%) of patients with at least one positively adjudicated pancreatic neoplasm by type: 1) malignant - confirmed, 2) Malignant - probable, 3) Benign.

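### SAP 2.3.5.1 lists only crude on-treatment percentages for the AESI and AERSM groupings (severe hypoglycemia excepted); the time-to-first-event dates in Appendix C have no matching output, and no on-study table uses these groupings

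*SAP*

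**What the plan says.** The AESI/AERSM part of SAP 2.3.5.1 states that "AESI and AERSM will be summarized during the TEAE period by prespecified- grouping" and preferred term, as number and percentage of participants. It sets no denominator of its own, so the rule under Generalities applies: "The denominator for computation of percentages is the safety population within each treatment group". SAP 2.1.4 (Observation period) defines the window as "the time from the first injection of the IMP to the last injection of the IMP + 30 days", with 7 days for hypoglycemia.

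Two categories have their own text. Severe hypoglycemia gets a percentage and also "Number of events per 100 patient-years of total IMP exposure". Pancreatic events get counts and percentages by type, introduced by "The following analysis will be provided for positively adjudicated events during the TEAE period".

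For the longer period, the SAP says that all AEs, SAEs, "AEs leading to permanent treatment discontinuation, and AEs leading to death will be summarized for the on-study period by SOC and PT". The AESI and AERSM groupings are not named there.

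Appendix C makes the first IMP date the start for time-to-first-event handling of AEs and names AESI and AERSM explicitly. It censors a participant without an AE at last IMP plus 30 days, or at death if earlier. Appendix B, in its adverse-event row, refers back to the AESI and AERSM section.

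**The concern.** The numerator is limited to time on IMP plus 30 days, while the denominator is everyone treated. An arm that stops IMP earlier is observed for less time, so its percentage falls even if the rate while treated is unchanged. For events that accrue over 24 to 36 months, such as pancreatic, renal, retinal or thyroid C-cell events, the comparison with placebo then mixes risk with length of observation.

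Earlier stopping on efpeglenatide is plausible. Protocol 2.3 reports that GI events leading to discontinuation of efpeglenatide in the three large Phase 2 studies "were 2.2%, 8.3% and 9.8%, respectively", and that discontinuations appeared to rise with dose. Safety of both doses is a stated secondary objective.

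There is also a gap in coverage. An event that meets a grouping definition more than 30 days after the last injection enters no planned grouping summary, although the protocol follows participants off IMP to the end of the study.

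**Working it through.** The documents state no figure for AESI or AERSM reporting, so there is no plan figure to reproduce. The check has two parts.

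**1. Which outputs exist for the groupings**

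| Place | What it gives | Covers AESI/AERSM groupings? |
|---|---|---|
| SAP 2.3.5.1, AESI/AERSM text | n (%), on-treatment window | Yes |
| SAP 2.3.5.1, severe hypoglycemia | n (%) and events per 100 patient-years | That category only |
| SAP 2.3.5.1, Kaplan-Meier | Nausea, vomiting, diarrhea | No; these are preferred terms at any severity |
| SAP 2.3.5.1, on-study and post-treatment tables | AEs and SAEs by SOC and PT | No |
| Appendix C | Start and censoring dates | Yes, but no output uses them |
| Appendix B | Pointer to the AESI/AERSM text | Leads back to n (%) |

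The on-study sentence refers to the analyses placed above it, and the AESI/AERSM text comes after it. The on-study SOC/PT tables cannot be regrouped by hand. SAP Table 2 builds the groupings from customized queries, severity, eCRF categories, a dedicated pancreatic page and an AESI tick-box, and adding PT rows counts some participants twice.

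**2. Size of the distortion**

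Assumptions, not document figures: placebo rate h0 = 0.01 per year; T = 2.4 years observed, within the planned 24–36 months; an extra share d = 0.05 to 0.10 of the efpeglenatide arm stops IMP at s = 0.25 to 0.5 years; constant rate h while treated. The 30-day tail is 30/365.25 = 0.082 years.

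Crude ratio = [(1 − d)(1 − exp(−hT)) + d(1 − exp(−h(s + 0.082)))] / (1 − exp(−h0·T)), with denominator 1 − exp(−0.024) = 0.02371.

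No true difference (h = 0.01):
- d = 0.05, s = 0.5: 0.95 + 0.05 × 0.00580/0.02371 = 0.96.
- d = 0.10, s = 0.25: 0.90 + 0.10 × 0.00332/0.02371 = 0.91.

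True rate ratio 1.25 (h = 0.0125; 1 − exp(−0.03) = 0.02955):
- d = 0.05, s = 0.5: (0.95 × 0.02955 + 0.05 × 0.00725)/0.02371 = 1.20.
- d = 0.10, s = 0.25: (0.90 × 0.02955 + 0.10 × 0.00414)/0.02371 = 1.14.

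Without extra stopping, the second case reads 0.02955/0.02371 = 1.246, so almost all of the shortfall comes from the stopping.

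A second model varies the assumptions: follow-up uniform over 2–3 years, 5% per year other stopping in both arms, early stopping at 2 months on efpeglenatide only, placebo rate 1 per 100 patient-years, true ratio 1.5. Mean time on IMP without early stopping is 2.348 years. With 9.8% stopping early, the exposure ratio is (0.098 × 0.167 + 0.902 × 2.348 + 0.082)/(2.348 + 0.082) = 2.217/2.430 = 0.912.

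| Early stopping, efpeglenatide only | Exposure ratio | Crude ratio (true 1.5) |
|---|---|---|
| 0% | 1.00 | 1.49 |
| 2.2% | 0.98 | 1.46 |
| 8.3% | 0.925 | 1.38 |
| 9.8% | 0.91 | 1.36 |

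At 8.3–9.8%, the share of the relative excess not shown is (1.5 − 1.38)/0.5 = 24% to (1.5 − 1.36)/0.5 = 28%. A rate per patient-year at risk, or a Kaplan-Meier or Cox analysis on the Appendix C dates, would return about 1.5 in this model.

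**The case against.** A reader might infer that the SAP handles these events only as crude percentages and would hide an excess risk on efpeglenatide. The documents do not support that, for three reasons.

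- Appendix C names AESI and AERSM for time-to-first-event handling, with censoring tied to exposure. The framework exists; the output is missing.
- Unequal stopping would be visible. SAP 2.2 plans Kaplan-Meier estimates of permanent treatment discontinuation, for any reason and for AEs, and SAP 2.3.3.1 reports exposure in patient-years. Later AEs and SAEs still appear by preferred term, and AESIs, SAEs and pancreatic events are listed individually.
- The direction is not established. The Phase 2 figures have no placebo comparator, and the 9.8% comes from a study in overweight or obese patients without diabetes. This trial titrates over up to 8 weeks, treats permanent stopping as a last resort and allows resumption.

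The size is also modest against sampling error. At 1% per year, about 1333 placebo participants give 1333 × 0.0237 ≈ 32 with an event, against about 60 in the pooled arms with no true difference. The standard error of the log ratio is √(1/32 + 1/60) ≈ 0.22, a 95% factor of about 0.65 to 1.54. The largest distortion above with no true difference, ln 0.914 = −0.09, is about 0.4 standard errors. Safety analyses are descriptive, so no formal test depends on this.

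These points limit the finding but do not remove it. Dividing by total patient-years is only approximate: exposure ends 7 days after the last dose rather than 30, and does not stop at the first event. The planned listings do not name AERSM as a class. A programmer working from 2.3.5.1 would produce only percentages for every grouping except severe hypoglycemia.

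**Conclusion.** The point holds as an internal gap with a cheap remedy. SAP 2.3.5.1 lists only crude on-treatment percentages for the groupings other than severe hypoglycemia. Appendix C defines dates for a better summary that nothing in 2.3.5.1 or Appendix B calls for. Late events have no display by grouping.

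The distortion is conditional. It needs unequal exposure, and it understates an excess only if efpeglenatide is stopped earlier than placebo. Under the assumptions shown, a true 1.25 reads 1.14–1.20 and equal risk reads 0.91–0.96. These figures rest on assumed event rates and an assumed excess of stopping that the documents do not supply. Events clustered in titration, such as severe GI events, are little affected.

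**What to change.** In SAP 2.3.5.1:

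1. For AERSM groupings that accrue over time (for example pancreatic events, acute renal failure, diabetic retinopathy complications, calcitonin increase and thyroid C-cell neoplasm) and for the ALT AESI, add by arm the participants with a first event per 100 patient-years at risk, or a Kaplan-Meier estimate. Use the Appendix C start and censoring dates, and refer to that appendix.
2. Repeat the AESI/AERSM grouping table, including adjudicated pancreatic events, for the on-study period.
3. Keep n (%) alone for early-clustering categories such as severe GI events, where a constant-rate summary can itself mislead.
4. List the new outputs in Appendix B.

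The two additions complement each other: the first adjusts for length of observation on IMP, and the second captures events after the window closes. Serious TEAEs need no added rate, since on-study SAE tables are already planned. The cost is SAP wording and a few descriptive tables from data already collected; no test or error rate changes.
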